5.2.2.3.17 Treatment Interruptions / Modifications

Radiotherapy should begin within 1 week ± 3 days after Cycle 1, Day 1. Treatment interruptions are to be avoided unless medically necessary. Missed treatments should be compensated for with a BID treatment delivered. This should be limited to a maximum of twice during the 6 weeks of treatment with a minimum of 2 days between BID treatments for AFX regimen and twice during the 7 weeks of treatment with a minimum of 2 days between BID for SFX regimen. Any breaks in RT should be minimized.

5.3 Surgery Guidelines

Neck imaging (MRI or CT scan) and FDG-PET scan will be performed at 12 weeks after the end of CRT + pembrolizumab/placebo to evaluate the neck for a potential neck dissection. A neck dissection will be recommended in case of persistent disease in the neck based on a positive FDG-PET scan [25]. Neck dissection should be performed by Week 16 after the last dose of CRT but no later than Week 20 after the end of CRT and according to standard guidelines at each center.

In case of PET-positivity of the primary site, an endoscopy has to be performed within 2 weeks and a biopsy taken from the suspicious lesion. Exceptions to this may be considered with Sponsor consultation. A salvage intervention will then be performed no later than 6 weeks after the endoscopy at the discretion of the treating head and neck surgeon and Multidisciplinary Team (MDT), if the subject is found fit for the chosen intervention and accepts the intervention and its potential complications and side effects.

5.3.1 Pre-operative Assessment

Subject's Charlson co-morbidity index, ASA-score, and nutritional status are recommended pre-operatively. Also, coagulation parameters and routine labs (CBC, chemistry profile, and coagulation tests) will be performed. In case of procedures with potential long-term swallowing compromise the treating surgeon may obtain pulmonary function tests. Subjects deemed unfit for the chosen procedure will not undergo salvage. This decision will be taken individually by the treating surgeon in close collaboration with the multidisciplinary team together with the subject, assuring that the goals of quality-of-life the subject wishes to obtain are met.

Pre-operative diagnostics are comprised of a CT scan with contrast, in case of questionable soft tissue involvement an additional MRI, in case of possible bone involvement a CT scan is mandatory. An MRI of the head and neck only will suffice, if clinically bone involvement can be affirmatively excluded. An endoscopy has to be performed pre-operatively in case a salvage of the primary site is planned. In case of a negative FDG-PET scan in the primary site, but positive FDG-PET scan in the neck, a neck dissection without endoscopy suffices. A histological diagnosis at the primary site for a salvage resection is mandatory.

All results should be discussed in the MDT to determine whether or not and to what extent a subject with a positive FDG-PET scan in the neck or histologically proven disease at the primary site should be operated on.

Endoscopies in case of positive FDG-PET scans at the primary site should be performed within 2 weeks of FDG-PET result; and if positive and accepted by the MDT for surgery, should be taken for salvage intervention no later than 6 weeks after the endoscopy. A neck dissection for a FDG-PET positive neck should be done within 4 weeks from the FDG-PET result but no later than 20 weeks after the last dose of CRT.

5.3.2 Surgical Procedure Guidelines

5.3.2.1 Technique of Anesthesia

For the endoscopy a regular general anesthesia according to institutional guidelines should be performed. The same accounts for neck dissections and salvage resections with or without reconstructions.

5.3.2.2 Technique of Surgical Procedure

5.3.2.2.1 Endoscopy

The endoscopy can comprise of an examination of the oral cavity, nasopharynx, oropharynx, larynx, hypopharynx, esophagus, and tracheobronchial system (upper airways). The instruments for this examination under general anesthesia are at the discretion of the performing surgeon. A representative biopsy has to be taken from the site at which recurrence is suspected. If biopsies are returned to be inconclusive, a re-biopsy has to be performed. Exceptions to this may be considered with Sponsor consultation.

5.3.2.2.2 Neck Dissection

The neck dissection has to be at minimum a selective neck dissection comprising of the neck levels containing the suspicious nodes and in addition one adjacent level. If in other words level 3 nodes are described positive on the FDG-PET scan, a level 2, 3, 4 selective neck dissection has to be performed. In case of involvement of the sternocleidomastoid muscle, the internal jugular vein, or the spinal accessory nerve, these structures then have to be removed in addition. The surgeon should describe in his operation report the extent of macroscopic disease. Incisions and instrumentation are at the discretion of the surgeon performing the procedure.

5.3.2.2.3 Salvage Resection of the Primary Site

Salvage procedures are tailored to the location of the recurrence. The resection at each site should provide margins of at least 5 mm in the primary specimen, unless there are surgical contra-indications i.e., proximity of great vessels. The choice of procedure as well as the choice of reconstruction, if deemed necessary, is at the discretion of the surgeon.

5.3.2.2.4 Complications After Salvage Procedures And/or Neck Dissections

Complications after salvage procedures and/or neck dissections are common, and every center has certain strategies to manage them. This refers to common complications like chylous fistulas, other pharyngeal fistulas after pharyngotomies, compromise of the spinal accessory nerve, other wound healing problems, etc. In the absence of guidelines for the management of those, it will be at the discretion of the treating surgeon to manage these complications to the best of his/her knowledge.

5.3.2.3 Post-operative Care

The post-operative care is closely related to the site of intervention. In general, all efforts should be made to de-cannulate subjects with tracheostomies as fast as possible and start the subject on an oral diet. It is critical that early on in the process of swallowing and speech rehabilitation speech pathologists get involved to work on a regular basis with the subject. It is also critical to mobilize the subject as fast as his/her condition allows. These decisions need to be taken by the treating head and neck surgeon and should be individualized to the subject's ability and needs. In case of a poor swallowing rehabilitation prognosis given by the speech pathologist of the individual center, a percutaneous gastrostomy (PEG) needs to be inserted.

5.3.2.4 Pathology Specimen

Biopsies taken from the subject during an endoscopy should be kept in formalin and transported to the pathologist.

The neck dissection specimen should be sent to the pathologist level by level. In other words, in case of a selective neck dissection level 2, 3, 4, the surgeon has to send every level separately to the pathologist. It is not necessary to orient these pieces.

The primary resection specimen in case of primary site salvage has to be sent as a whole and oriented with either sutures or colors. A free margin is hereby considered to be ≥ 5 mm, a close margin considered to be between 1-5 mm, and a positive margin considered to be <1 mm in the primary resection specimen. If additional resections based on frozen sections are done that are considered to be part of the primary resection, these pieces have to be oriented and either sutured to the main specimen or the new true margin has to be marked through inking and the pathologist informed.

Communication from surgeon to pathologist, transport, processing (time to freezing) and reporting of the specimen should follow local practice and institutional guidelines.

Remaining tissue is required to be sent to the central laboratory (see central laboratory manual). If invasive cancer is not found at time of biopsy or surgery that was performed on study, tissue does not need to be sent to central laboratory for biomarker testing.

5.3.2.5 Evaluation of Post-Operative Complications

Surgical complications will depend on the extent of the procedures, the site of intervention, and the technique of reconstruction. Given the variety of possible interventions a large variety of complications have to be foreseen.

5.3.2.5.1 Timing of Assessment of Complications and Mortality

Complications and mortality as a consequence of the surgical procedures will be assessed and reported as described in Sections 5.3.2 and 5.3.2.5.1. All AEs considered to be post-surgical complications by the investigator from time of protocol-specified surgery through 30 days following surgery must be reported by the investigator to the Sponsor. All AEs meeting serious criteria considered to be post-surgical complications by the investigator from the time of protocol-specified surgery through 90 days following surgery or 30 days if the subject initiates new anticancer therapy, whichever is earlier, must be reported by the investigator to the Sponsor.

The reporting has to include all measures taken to manage the complication that includes operative or endoscopic interventions and all diagnostics deemed necessary.

5.3.2.5.2 Identification and grading of complications

The following tables ([Table 12](#), [Table 13](#), and [Table 14](#)) provide the identification and grading of post-operative complications (but not limited to):

Table 12 Endoscopy

Endoscopy:	
Dysphagia	Grade 1-3
Odynophagia	Grade 1-3
Voice changes and hoarseness	Grade 1-3
Dyspnea	Grade 1-5
Teeth damage	Grade 1-3
Esophageal perforation	Grade 4
Mediastinitis	Grade 4

Table 13 Neck Dissection

Neck Dissection:	
Bleeding	Grade 1-5
Infection	Grade 1-5
Wound healing complication	Grade 1-5
Spinal accessory nerve damage	Grade 1-3
Hypoglossal nerve damage	Grade 1-3
Vagal nerve damage	Grade 1-3
Phrenic nerve damage	Grade 1-3
Sympathetic trunk damage (Horner syndrome)	Grade 1-3
Chyle leak	Grade 1-3

Table 14 Salvage Surgery at Primary Site with or Without Reconstruction

Salvage at Primary Site with or Without Reconstruction (Free or Regional/local Flap):	
Bleeding	Grade 1-5
Infection	Grade 1-5
Fistula	Grade 1-5
Wound healing complication	Grade 1-5
Dysphagia	Grade 1-3
Odynophagia	Grade 1-3
Trismus	Grade 1-3
Loss of voice and hoarseness	Grade 1-3
Partial or total flap loss	Grade 1-5

5.4 Trial Blinding

Pembrolizumab or placebo will be prepared by the unblinded pharmacist and dispensed in a blinded fashion by an unblinded pharmacist or qualified trial site personnel. The subject, the investigator who is involved in the treatment or clinical evaluation of the subjects and the Sponsor are unaware of the group assignments. See Section 7.1.7.2 Subject Blinding/Unblinding, for a description of the method of unblinding a subject during the trial, should such action be warranted.

5.5 Randomization or Treatment Allocation

Randomization will occur centrally using an interactive voice response system / integrated web response system (IVRS/IWRS). Subjects will be assigned randomly in a 1:1 ratio to receive either pembrolizumab or placebo in combination with chemotherapy and radiation.

RT regimen per subject will be assigned by the site through IVRS prior to randomization to ensure subjects are balanced between the arms with respect to type of RT regimen selected.

5.6 Stratification

Treatment allocation/randomization will be stratified according to the following factors:

1. Radiotherapy Regimen (AFX or SFX)

2. Tumor site/p16 status: 2 levels (Oropharynx – p16 positive vs. Oropharynx – p16 negative or larynx/hypopharynx/oral cavity HNSCC)
3. Stage III vs. Stage IV

5.7 Concomitant Medications/Vaccinations (Allowed & Prohibited)

Medications or vaccinations specifically prohibited in the exclusion criteria are not allowed during the ongoing trial. If there is a clinical indication for any medication or vaccination specifically prohibited during the trial, discontinuation from trial therapy or vaccination may be required. The investigator should discuss any questions regarding this with the Sponsor Clinical Director. The final decision on any supportive therapy or vaccination rests with the investigator and/or the subject's primary physician. However, the decision to continue the subject on trial therapy or vaccination schedule requires the mutual agreement of the investigator, the Sponsor and the subject.

5.7.1 Acceptable Concomitant Medications

All treatments that the investigator considers necessary for a subject's welfare may be administered at the discretion of the investigator in keeping with the community standards of medical care. All concomitant medication will be recorded on the case report form (CRF) including all prescription, over-the-counter (OTC), herbal supplements, and IV medications and fluids. If changes occur during the trial period, documentation of drug dosage, frequency, route, and date should also be included on the CRF.

Supportive care is permitted for managing drug-related toxicities. See guidelines in Section 5.8. All prior/concomitant medications received within 28 days before the first dose of trial treatment through 30 days after the last dose of trial treatment should be recorded. Concomitant medications administered after 30 days after the last dose of trial treatment should be recorded for SAEs and ECIs as defined in Section 7.2.

5.7.2 Prohibited Concomitant Medications

Subjects are prohibited from receiving the following therapies during the Screening and Treatment Phase of this trial:

- Antineoplastic systemic chemotherapy or biological therapy;
- Immunotherapy not specified in this protocol;
- Chemotherapy not specified in this protocol;
- Radiation therapy not specified in this protocol;
- Investigational agents other than pembrolizumab/placebo.
- Administration of palliative radiation therapy will be considered clinical progression for the purposes of determining EFS.
- Live vaccines within 30 days prior to the first dose of trial treatment and while participating in the trial. Examples of live vaccines include, but are not limited to, the following: measles, mumps, rubella, chicken pox, yellow fever, rabies, BCG, and typhoid

(oral) vaccine. Seasonal influenza vaccines for injection are generally killed virus vaccines and are allowed. However, intranasal influenza vaccines (e.g., Flu - Mist®) are live attenuated vaccines, and are not allowed.

- Systemic glucocorticoids for any purpose other than to modulate symptoms from an adverse event of suspected immunologic etiology. The use of physiologic doses of corticosteroids may be approved after consultation with the Sponsor.
 - Note: A short course of steroids may be used as concomitant medication for either treatment of an adverse event or medical condition with Sponsor approval.
 - Note: Inhaled steroids are allowed for management of asthma.
 - Note: Use of prophylactic corticosteroids to avoid allergic reactions (e.g., to IV contrast dye) is permitted.
 - Note: Use of steroids for antiemetic purposes is permitted.
 - Note: Use of steroids for premedication for trial treatment is permitted.
- No prophylactic growth factor support such as erythropoietin or granulocyte-colony stimulating factor is allowed during chemoradiation treatment. An exception is that treatment of neutropenia with granulocyte-colony stimulating factor is allowed, if clinically indicated.
- During cisplatin treatment only: Cisplatin is a potentially nephrotoxic drug which can be potentiated by other nephrotoxic agents such as aminoglycoside antibiotics. Use of aminoglycosides (such as streptomycin, dihydrostreptomycin, kanamycin, gentamicin, neomycin, tobramycin, netilmicin, and amikacin) should be administered with caution given the risk of nephrotoxicity. The serum creatinine, blood urea nitrogen (BUN), and electrolytes should be monitored carefully when additional nephrotoxic agents are used. Subjects receiving cisplatin and other potentially ototoxic drugs, such as aminoglycosides, should also be closely monitored for signs of ototoxicity. If the administration of aminoglycosides is required, additional audiometric testing may be necessary for further safety monitoring. Please contact the Sponsor if aminoglycosides are administered to a study subject in order to discuss renal management as well as frequency of audiometric assessments.

Subjects who, in the assessment by the investigator, require the use of any of the aforementioned treatments for clinical management should be removed from the trial. Subjects may receive other medications that the investigator deems to be medically necessary.

The Exclusion Criteria describes other medications that are prohibited in this trial.

There are no prohibited therapies in the Post-Treatment Follow-up Visits.

5.8 Rescue Medications & Supportive Care

5.8.1 Supportive Care Guidelines for Pembrolizumab/Placebo

Subjects should receive appropriate supportive care measures as deemed necessary by the treating investigator. Suggested supportive care measures for the management of AEs with potential immunologic etiology are outlined along with the dose modification guidelines in Section 5.2.1.2, **Table 3**. Where appropriate, these guidelines include the use of oral or IV treatment with corticosteroids, as well as additional anti-inflammatory agents if symptoms do not improve with administration of corticosteroids. Note that several courses of steroid tapering may be necessary as symptoms may worsen when the steroid dose is decreased. For each disorder, attempts should be made to rule out other causes such as metastatic disease or bacterial or viral infection, which might require additional supportive care. The treatment guidelines are intended to be applied when the Investigator determines the events to be related to pembrolizumab.

Note: If after the evaluation of the event, it is determined not to be related to pembrolizumab, the Investigator does not need to follow the treatment guidance.

It may be necessary to perform conditional procedures such as bronchoscopy, endoscopy, or skin photography as part of evaluation of the event.

5.8.2 Supportive Care Guidelines for Cisplatin

See Section 5.2.2 - Timing of Dose Administration

5.8.3 Supportive Care Guidelines for Radiation

Radiation-induced head and neck toxicity is well known and has been well described. It is expected to vary according to the total dose and the concomitant use of chemotherapy. Locoregional toxicity will be monitored during treatment using the CTCAE v4.0 scaling system and will be reported in the CRFs.

Reversible mucositis and pharyngitis is expected, and supportive care will be initiated (e.g., pain killers, mouth wash, adaptation of the diet, use of a nasogastric or percutaneous endoscopic gastrostomy feeding tube). In very rare cases of severe Grade 4 mucositis (e.g., bleeding), it may be necessary to interrupt RT for a few days. However, it is important to limit the break to a strict minimum.

Various degrees of skin reaction (typically Grade 2, less frequently Grade 3) are expected in the treated area. Other expected acute reactions include fatigue, xerostomia, dysgeusia, ageusia and dysphagia.

Central nervous system events in terms of nausea and vomiting are expected and may be managed with an NK-1 receptor antagonist such as (aprepitant, aloxi, zofran, or compazine) per local standards of care and local product label. Late effects include some degree of xerostomia and occasionally persistent dysphagia and may be managed according to local standards of care.

Mandibular osteoradionecrosis may occur in less than 5% of the subjects. A thorough dental evaluation and adequate care must be performed prior to the start of radiotherapy to substantially decrease this risk.

5.9 Diet/Activity/Other Considerations

5.9.1 Diet

Subjects should maintain a normal diet unless modifications are required to manage an AE such as diarrhea, nausea or vomiting.

Insertion of feeding tube is allowed for nutritional purposes and, if procedure is performed as a planned hospitalization, would not meet that criterion for SAE.

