7.2.4.3 Protocol-Specific Exceptions to Serious Adverse Event Reporting

Efficacy endpoints as outlined in this section will not be reported to the Sponsor as described in Section 7.2.3.

Specifically, the suspected/actual events covered in this exception include any event that is disease progression of the cancer under study.

The Sponsor will monitor unblinded aggregated efficacy endpoint events and safety data to ensure the safety of the subjects in the trial. Any suspected endpoint which upon review is not progression of the cancer under study will be forwarded to global safety as an SAE within 24 hours of determination that the event is not progression of the cancer under study.

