Seriousness		
A serious adverse event is any adverse event occurring at any dose or during any use of Sponsor's product that:
 
†Results in death; or
 
†Is life threatening; or places the subject, in the view of the investigator, at immediate risk of death from the event as it occurred (Note: This does not include an adverse event that, had it occurred in a more severe form, might have caused death.); or
 
†Results in a persistent or significant disability/incapacity (substantial disruption of one's ability to conduct normal life functions); or
 
†Results in or prolongs an existing inpatient hospitalization (hospitalization is defined as an inpatient admission, regardless of length of stay, even if the hospitalization is a precautionary measure for continued observation. (Note: Hospitalization for an elective procedure to treat a pre-existing condition that has not worsened is not a serious adverse event. A pre-existing condition is a clinical condition that is diagnosed prior to the use of a MSD product and is documented in the patient's medical history.); or
 
†Is a congenital anomaly/birth defect (in offspring of subject taking the product regardless of time to diagnosis); or
 
Is a new cancer (that is not a condition of the study) (although not serious per ICH definition, is reportable to the Sponsor within 24 hours to meet certain local requirements); or
 
Is an overdose (whether accidental or intentional). Any adverse event associated with an overdose is considered a serious adverse event for collection purposes. An overdose that is not associated with an adverse event is considered a non-serious event of clinical interest and must be reported within 24 hours.
 
Other important medical events that may not result in death, not be life threatening, or not require hospitalization may be considered a serious adverse event when, based upon appropriate medical judgment, the event may jeopardize the subject and may require medical or surgical intervention to prevent one of the outcomes listed previously (designated above by a †).

Duration		Record the start and stop dates of the adverse event. If less than 1 day, indicate the appropriate length of time and units
Action taken		Did the adverse event cause the Sponsor's product to be discontinued?

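### Section 5.9.1 waives the hospitalization criterion for every planned feeding-tube admission, including one caused by an on-study adverse event, which Table 23 does not exempt

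*Combined protocol and SAP*

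**What the plan says.** Section 5.9.1 (Diet) states: "Insertion of feeding tube is allowed for nutritional purposes". It adds that the insertion, "if procedure is performed as a planned hospitalization, would not meet that criterion for SAE". The criterion meant is inpatient hospitalization. The section does not define a planned admission, and it does not ask why the tube is needed. Section 5.2.2.2 has a parallel sentence for planned cisplatin hydration admissions.

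Table 23 in Section 7.2.5 defines seriousness. One criterion reads: "Results in or prolongs an existing inpatient hospitalization (hospitalization is defined as an inpatient admission, regardless of length of stay". Its carve-out for elective procedures is narrow: "Hospitalization for an elective procedure to treat a pre-existing condition that has not worsened is not a serious adverse event". The table adds: "A pre-existing condition is a clinical condition that is diagnosed prior to the use of a MSD product".

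Other sections link tubes to toxicity. Sections 5.8.3 and 5.2.2.3.16 list, among supportive care for expected mucositis and pharyngitis, "use of a nasogastric or percutaneous endoscopic gastrostomy feeding tube". Section 5.3.2.3, on post-operative care, says that when the swallowing prognosis is poor "a percutaneous gastrostomy (PEG) needs to be inserted".

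Section 7.2.4.3, whose title announces protocol-specific exceptions to SAE reporting, says that "the suspected/actual events covered in this exception include any event that is disease progression of the cancer under study". It names no procedural admission and does not refer to 5.9.1.

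**The concern.** A feeding tube can be placed in advance as a precaution, or because the patient can no longer eat. In the first case nothing untoward has led to the admission. In the second, the admission results from an AE, which is what the hospitalization criterion is meant to capture. Section 5.9.1 treats both alike, provided the admission was planned.

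Comparing safety and tolerability is a secondary objective, and mucosal and swallowing toxicity is expected with this chemoradiation. In the interim safety report of the earlier combination study described in Section 4.1.4, dysphagia was one of the two most commonly reported AEs. If sites differ on whether 5.9.1 or Table 23 governs, the same clinical course can be reported within 24 hours as an SAE at one site and recorded as a non-serious AE at another. Whether the bed was booked, rather than the toxicity, would then settle the classification.

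**Working it through.** No sample size, event count or error rate is involved, so the check sets the passages side by side.

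**Scope of each rule**

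| Question | Section 5.9.1 | Table 23 |
|---|---|---|
| What is waived? | The hospitalization criterion only | The hospitalization criterion only |
| For which admissions? | Any planned admission for a nutritional feeding tube | An elective procedure for a condition that existed before the sponsor's product and is stable |
| Does it cover a toxicity that arose on treatment? | Not excluded | Not covered |

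**Three cases**

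1. *Planned tube admission with no new or worsened AE behind it.* No AE has led to the admission, so Table 23 has nothing to classify. The two passages agree.
2. *On-study AE leads to a booked tube admission, with no other seriousness criterion met.* Under Table 23 the event is serious: there is an inpatient admission, and the pre-existing-condition carve-out fails because the AE is new or has worsened. Under 5.9.1 the hospitalization criterion is not met, so the event is not serious. The answers are opposite.
3. *As case 2, but the admission was unplanned, or the event was life-threatening, disabling or judged an important medical event.* The event is serious under both, because 5.9.1 waives one criterion and only for planned admissions.

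The conflict is therefore confined to case 2. The protocol foresees the ingredients of that case. Sections 5.8.3 and 5.2.2.3.16 use tubes for mucositis and pharyngitis, Section 5.3.2.3 calls for a PEG after surgery when swallowing prognosis is poor, and Table 14 lists dysphagia among the complications of salvage surgery. Section 7.2.4.1 requires serious post-surgical complications to be reported, so a post-operative PEG admission can fall under both rules.

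**What depends on the classification**

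- *Reporting.* Under 7.2.4.1, SAEs from randomization to 90 days after treatment (30 days if new anticancer therapy starts) go to the Sponsor within 24 hours. Case 2 events fall in or out according to the rule followed.
- *SAE summaries.* In Table 26, the any-serious-AE row, the serious-and-drug-related row and the specific serious AE rows all use seriousness and all change.
- *Comparison of toxicity.* Specific Grade 3-5 AEs at 5% or more in an arm, and specific AEs of any grade at 10% or more, are Tier 2 with a 95% confidence interval whether serious or not. These rows do not change.
- *Recording and grading.* Section 7.2 requires all AEs, serious or not, through 30 days after treatment, and 7.1.2.1 extends grading and recording into follow-up. Neither depends on seriousness.

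**The case against.** The strongest reply is that 5.9.1 is a deliberate, specific carve-out. It waives one criterion and leaves the others open, and 5.2.2.2 uses the same device for hydration. On this view a specific rule overrides a general one, and the silence of 7.2.4.3 means little because that section is about efficacy endpoints. Part of this stands: 7.2.4.3 is weak evidence of contradiction, and 5.9.1 does not remove SAE status as such. But no text gives 5.9.1 precedence over Table 23. The hydration analogy is also imperfect, because planned hydration is scheduled preventive support, whereas a tube admission can be the result of the AE itself. The important-medical-event route does not restore consistency either, because it is discretionary.

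A second reply is that the signal is not lost. This stands. The toxicity is still recorded and graded, the external monitoring committee's periodic reviews cover AEs and not only SAEs, and the physical examinations cover feeding-tube presence. The QLQ-H&N35 has a feeding-tube item, and swallowing is a secondary patient-reported outcome. A reader might infer that a swallowing or mucosal term would lose its between-arm confidence interval. The documents do not support that: a serious-AE row could fall below its 5% threshold, but a Grade 3-5 term at 5% or more keeps its interval.

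Third, the fix would not make seriousness independent of site practice, since under Table 23 an outpatient placement does not meet the hospitalization criterion and an inpatient one does. That is true, but it is a feature of the criterion generally and not a contradiction within the protocol.

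Fourth, the current amendment follows the final efficacy analysis, and study treatment lasted about one year, so a prospective change reaches few admissions from the chemoradiation period. That also stands, and it moves the weight of the fix to checking recorded cases. Later events remain in scope: 5.9.1 has no time limit, treatment-related serious late toxicity is followed for up to 5 years, and 5.8.3 names persistent dysphagia as a late effect.

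**Conclusion.** The concern holds in a limited form. For a planned feeding-tube admission that results from a new or worsened AE and meets no other seriousness criterion, 5.9.1 and Table 23 give opposite answers, and nothing says which governs. Followed literally, 5.9.1 keeps such events out of 24-hour reporting and the SAE tables, contrary to the protocol's own definition. That is more than missing detail, and it should be corrected.

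The size is unknown. The documents give no rate of tube admissions, planned or otherwise, and no split by reason for placement, so neither the number of affected subjects nor the shift in any SAE percentage can be derived.

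Two stronger readings should be resisted. A reader might take 5.9.1 to say that a tube admission can never be an SAE; it waives only the hospitalization criterion. A reader might also infer that the treatment comparison is biased; sites are blinded, and nothing in the documents suggests that booking practice would differ by arm. The demonstrated harm is inconsistent classification and possible under-reporting of SAEs.

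The conclusion assumes that the waiver applies as worded to toxicity-driven placement. If the Sponsor has instructed sites otherwise outside these documents, the gap is one of wording only. The statement that recording is unaffected rests, for events more than 30 days after treatment, on Section 7.1.2.1.

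**What to change.** Reconcile 5.9.1 with 7.2.4.1 and Table 23:

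- Limit the 5.9.1 waiver to planned feeding-tube admissions that do not result from a new or worsened AE. State that an admission for a tube because of new or worsened mucositis, dysphagia or a post-surgical complication is judged under Table 23.
- Cross-refer to the narrowed waiver from the SAE section, for example in 7.2.4.3, so that a site finds one rule.
- Check tube admissions already recorded against Table 23, using the feeding-tube information from the physical examinations to help find them. Correct the seriousness classification where needed.

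The cost is a short amendment, somewhat more SAE reports, and the retrospective check. With the final efficacy analysis complete, the new wording would mostly affect late events; the check covers the treatment period. No efficacy analysis changes.
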